### 2.3.2. Handling of Key Milestone Dates

- Trial reference start date (Day 1): the first double-blind dose date for each subject (First dose date). If missing or incomplete, the first dose date will be imputed as the randomization date.
- Last dose date: the date on which the last dose of double-blind study drug was taken by the subject. If only the day is missing, impute the last day of the month. If the month or the year is missing, impute the date as the date of the scheduled visit subsequent to the last visit when the study drug was dispensed. The imputed last dose date should be no later than the end of treatment visit date or the last trial contact date. In addition, the imputed last dose date should be no earlier than the first dose date. The last dose date is the date of permanent study drug discontinuation regardless of any temporary drug interruption.
- Last trial contact date: the date when the last trial-related procedure is conducted. It is defined as the latest of:
  - The date of last visit (scheduled or unscheduled visit; office or phone visit), or
  - The latest known date of an adverse event (AE) or the study endpoint event status, concomitant medication, vital sign measurements or laboratory results as reported on their respective electronic case report form (eCRF), or
  - The date of alternate contact made (eg, family members, relatives, friends, health care providers, public search) confirming the subject's survival status at the time of the GTED.

- For subjects who die during the study, the last trial contact date will be defined as the date of death.

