9.1.6. Post-Randomization Follow-up for Participants Unable to Attend Scheduled Visits

Subjects who are no longer able to continue to attend clinic visits for scheduled follow-up must have an alternate follow-up plan put in place. The options for this follow-up include:

- Less frequent clinic visits (eg, annual or to coincide with other care)
- Telephone, e-mail, letter, social media, fax, or other contact with the subject
- Telephone, e-mail, letter, social media, fax, or other contact with relatives of the subject
- Telephone, e-mail, letter, social media, fax, or other contact the subject's physicians (family or specialist)
- Review of any available medical records

These alternate follow-up methods should be planned to coincide with the visit times outlined in Time and Events schedule. Wherever possible follow-up should be made at least once each year and in very rare cases where this cannot be achieved arrangements must be made to follow-up with the participant at the scheduled completion of the study. Details regarding discussions via telephone, email, or other such contacts must be properly documented in source records, including responses by the subject.

If all means of follow-up fail, at a minimum, the site must attempt to collect vital status data, as noted in Section 10.5, Circumstances for Reduced Follow-up, by consulting family members, the subject's physicians and medical records, or public records, including the use of locator agencies as permitted by local law.

In the rare instance that a site closes for operational, financial or other reasons and subjects are unable to be contacted regarding site closure, data from that site will be transferred to another site for a check of public records and/or vital status (at a minimum).

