10.5. Circumstances for Reduced Follow-up

There may be circumstances in which a reduced follow-up schedule is required and the options for this are described in Section 9.1.6, Post-Randomization Follow-up for Participants Unable to Attend Scheduled Visits. If one of these regimens is not possible, it will be necessary for the site investigator to contact the Sponsor representative to indicate the reasons why no further follow-up is necessary. It is important to note that a subject declining further follow-up does not constitute withdrawal of consent and the alternate follow-up mechanisms that the participant agreed to when signing the consent form will still apply (eg, searches of databases, use of locator agencies at study completion) as permitted by local regulations.

In this regard, the subject will be asked as a condition of entry into the study to agree to grant permission for the investigator to consult family members, the subject's physicians and medical records, or public records, including the use of locator agencies as permitted by local law, to determine the subject's status with respect to the CV safety composite endpoint, in the event the subject is not reachable by conventional means (eg, office visit, telephone, e-mail, or certified mail). The subject is also to be advised that if the site of the study doctor closes, and the study doctor cannot reach the subject to inform him/her, the contact information will be transferred to another site where a new study doctor will consult with family members, the subject's physicians

and medical records, or public records, including the use of locator agencies as permitted by local law, to determine the subject's endpoint status.

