**Table 1: Summary of Analysis Sets**

Analysis Set	Analysis Population	Data Period
ITT	Randomized subjects	Day 1 to the last trial contact date (see Section 2.3.2) up to the GTED
On-Study	Treated subjects	Day 1 to the last trial contact date (see Section 2.3.2) up to GTED
On-Treatment	Treated subjects	Day 1 to the last dose date (see Section 2.3.2) plus X a days or the last trial contact date, whichever is earlier.

a X is 2 days for laboratory (except ACR) and vital sign measurements, and 30 days for CV and mortality endpoints, and adverse events (AEs).

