## 2.3. Data Handling

### 2.3.1. Censoring Rules

For each analysis set, events that occur any time during the data period of the corresponding analysis set (see Table 1) will be considered as eligible events; otherwise subjects not experiencing an event will be censored at the earlier of the last trial contact day or end of the respective data period, if not otherwise specified.

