#### 4.2.2.1. The Composite of CV Death or Hospitalization for Heart Failure

The analysis will be based on time to the first occurrence of the composite event using ITT analysis set. The hazard ratio of canagliflozin compared to placebo and its 95% CI will be estimated using a stratified Cox proportional hazards regression model with treatment as the explanatory variable and history of CV disease (secondary and primary prevention) as the stratification factor. The p-value from the stratified log rank test for the treatment effect will also be reported.

The subgroup analysis will be conducted using the same approaches described in Section 4.1.3 and the following subgroups:

- Age group: <65, ≥65 years old;
- Sex: Male, Female;
- Race: White, Black or African American, Asian, Other;
- Region: Central/South America, Europe, North America, Rest of the World;
- Baseline BMI categories (<30, ≥30 kg/m^2);
- Baseline composite blood pressure categories ([SBP <140 or DBP <90 mmHg] vs. [SBP ≥140 and DBP ≥90 mmHg]);
- Baseline eGFR categories (30 to <60, 60 to <90, ≥90 mL/min/1.73m^2);
- Baseline HbA1c ≥ 8%: Yes/No;
- Duration of diabetes ≥ 10 years: Yes/No;
- History of CV disease: Yes/No;
- History of peripheral vascular disease: Yes/No;

---

a Undetermined death is considered CV death.

- History of amputation: Yes/No;
- Baseline use of statin;
- Baseline use of anti-thrombotics;
- Baseline use of RAAS inhibitor;
- Baseline use of Beta blocker;
- Baseline use of insulin;
- Baseline use of diuretics.

[figure not shown]

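### A contact that confirms only survival sets the censoring date for CV death/heart-failure hospitalization and for MACE, so time not observed for nonfatal events counts as event-free; the effect is probably small

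*SAP*

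**What the plan says.** SAP Table 1 runs the ITT data period from "Day 1 to the last trial contact date (see Section 2.3.2) up to the GTED". SAP 2.3.1 adds the default that "subjects not experiencing an event will be censored at the earlier of the last trial contact day or end of the respective data period", unless another rule is given.

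SAP 2.3.2 builds the last trial contact date from three kinds of date: the last visit (office or phone), the last date in the eCRF for adverse events, endpoint status, medication, vital signs or laboratory results, and an alternate contact such as relatives, care providers or "public search) confirming the subject's survival status at the time of the GTED". The rule for combining them is "It is defined as the latest of".

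For the first secondary endpoint, SAP 4.2.2.1 says: "The analysis will be based on time to the first occurrence of the composite event using ITT analysis set". It gives no censoring rule of its own. Neither do SAP 5.1.1 and 5.1.2 for MACE and its components.

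On conduct, Protocol 9.1.6 lists several alternate follow-up routes and then sets a floor: "If all means of follow-up fail, at a minimum, the site must attempt to collect vital status data". Protocol 10.5 asks subjects to permit searches of relatives, physicians, records and public sources "to determine the subject's status with respect to the CV safety composite endpoint" if they become unreachable.

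**The concern.** A censoring date should be the last date on which the event, had it happened, would have been known. A registry hit showing that someone is alive meets that standard for death. It does not meet it for a heart-failure admission, a nonfatal MI or a nonfatal stroke. Because the date is the latest of the three kinds, a survival-only contact overrides the earlier date on which endpoint status was really known. The subject then stays in the risk set for nonfatal events through time nobody observed.

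The SAP follows the right principle for the primary endpoint: SAP 4.1.2 censors at the last ACR measurement. The first secondary endpoint, which belongs to the confirmatory testing sequence, has no such rule.

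At stake are slightly understated absolute rates in both arms and, if survival-only time is unequal by arm, a hazard ratio that moves in favour of the arm with more of it. The planned outputs would not isolate the problem. SAP 3.3 counts subjects without final vital status, but a survival-only subject has a final vital status.

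**Working it through.** **Plan's own figures.** The documents state no event rate, event count or power for heart-failure hospitalization, the CV composite or MACE in this study, and no loss-to-follow-up proportion. The only sizing calculation (Protocol 11.2) concerns albuminuria. It reproduces: with 693 events and a hazard ratio of 0.78, √(693/4) × |ln 0.78| − 1.96 = 13.16 × 0.2485 − 1.96 = 1.31, which gives 90.5% power. It has no bearing on this point.

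**Step 1: trace the rule.** Default censoring at last trial contact (2.3.1) → latest of three kinds of date, one needing survival only (2.3.2) → no override for the composite (4.2.2.1) or MACE (5.1.1, 5.1.2). The rule suits CV death alone (4.2.2.2).

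**Step 2: one subject.** Last assessed for events at Week 52, found alive by public search at Week 156. Credited: 156 weeks free of nonfatal events. Unobserved: 156 − 52 = 104 weeks, or 104/156 = 67%. Censoring at last event ascertainment gives 52 weeks.

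**Step 3: trial-level person-time (assumed inputs).** N = 5,812 is from SAP 1.1. Assumed: 1 to 5% of subjects survival-only, 0.5 to 1.5 unobserved years each, mean follow-up 2.1 years, 0.5 to 1.0 heart-failure hospitalizations per 100 subject-years.

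- Total: 5,812 × 2.1 = 12,205 subject-years.
- Unobserved, low: 5,812 × 0.01 × 0.5 = 29; 29/12,205 = 0.2%.
- Unobserved, high: 5,812 × 0.05 × 1.5 = 436; 436/12,205 = 3.6%.
- Unseen hospitalizations: 29 × 0.005 = 0.1 to 436 × 0.010 = 4.4, so about 0.1 to 4.

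This gives lost subjects the same event rate as the rest. A higher rate would raise the count in proportion.

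**Step 4: hazard ratio.** Let u be the share of an arm's person-time covered by vital status only. The heart-failure rate in that arm is understated by the factor (1 − u). The heart-failure hazard ratio (canagliflozin over placebo) is multiplied by (1 − u_c)/(1 − u_p). If a share s of first composite events is heart failure and deaths are still captured, the composite is multiplied by (1 − s·u_c)/(1 − s·u_p).

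| u placebo | u canagliflozin | Heart failure | Composite, s = 0.3 | Composite, s = 0.5 |
|---|---|---|---|---|
| 3% | 3% | 1.000 | 1.000 | 1.000 |
| 3% | 1% | 0.99/0.97 = 1.021 | 1.006 | 1.010 |
| 5% | 2% | 0.98/0.95 = 1.032 | 1.009 | 1.015 |
| 1% | 3% | 0.97/0.99 = 0.980 | 0.994 | 0.990 |

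The equal-u row assumes equal component hazard ratios. If they differ, equal u reweights the composite a little: with assumed hazard ratios of 0.7 (heart failure) and 0.9 (CV death), equal shares and u = 5%, it becomes (0.45 + 0.35 × 0.95)/(0.5 + 0.5 × 0.95) = 0.803 instead of 0.800.

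**The case against.** The strongest reply is that very few subjects can be affected. Hospitalized heart failure goes to adjudication (Protocol 9.2). Serious adverse events, which include nearly all hospitalizations, are reported until study completion, also for subjects who withdraw early (12.2.1, 12.2.2). The post-treatment schedule collects CV events. Protocol 9.1.6 offers contact with physicians and review of records, with follow-up at least yearly where possible. This stands: stopping study drug does not by itself expose a subject to the problem, and the planned 10% annual treatment discontinuation is not the affected fraction.

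A reader might infer from Protocol 10.5 that follow-up of lost subjects was never extended to heart failure, because it names the CV safety composite, which Section 12 spells out as CV death, nonfatal MI and nonfatal stroke. The documents do not support that. The phrase states the purpose of a consent permission. Footnote b of the Time and Events Schedule describes tracing of lost participants by all reasonable means, without naming an endpoint, and the provisions above cover heart failure while any event contact continues. Record review is, however, permitted rather than required.

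A second reply is that censoring the composite earlier discards CV deaths found later by search. That is a real trade-off, and the reason for showing both rules. A third is that in this SAP MACE is a safety analysis, while the gatekeeping MACE test belongs to the integrated SAP, which is not among these documents. That also stands, so no claim is made about that test.

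**Conclusion.** The point holds for the SAP rule as written: a survival-only contact sets the censoring date for CV death/heart-failure hospitalization and for MACE and its nonfatal components. It is confined to subjects for whom every route other than a vital-status check failed. For MI and stroke it is narrower still, since Protocol 10.5 does seek that status; it arises only when the search yields survival alone.

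The size rests on assumptions, because the documents supply neither a count nor a heart-failure rate. It is probably small: about 0.2 to 3.6% of subject-years and about 0.1 to 4 hospitalizations. In the examples of unequal loss the composite hazard ratio moves about 0.6 to 1.5%, in either direction; with equal loss it hardly moves. A reader might infer a bias in favour of canagliflozin, but nothing in the documents indicates which arm would have more survival-only time, or that the arms would differ. The case for acting is that a stated rule miscounts time at risk for a confirmatory endpoint and is cheap to correct.

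**What to change.** **SAP 2.3.2.** Define a second date: the last date on which nonfatal event status was obtained, by visit, phone or email CV-event review, or physician or medical-record review. Keep the survival-inclusive date for CV death and all-cause death.

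**SAP 2.3.1, 4.2.2.1, 5.1.1 and 5.1.2.** For CV death/heart-failure hospitalization, MACE and the nonfatal components, censor subjects who are alive and event-free at the event-status date.

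**Deaths.** State that a death reported during ongoing scheduled follow-up counts as ascertained and stays in the composite. CV deaths found only by search after event contact was lost stay in the CV death analysis and in a companion analysis of the composite under the current rule. Counting such deaths while cutting the time of comparable survivors would itself bias the estimate, so events and time should share one window.

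**Reporting.** Give, by arm, the number of subjects and the subject-years between the two dates, and the results under both rules. State before unblinding that the event-status version carries the test.

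**Protocol 10.5 (secondary).** Where existing consent and local law allow, record and physician searches should also ask about hospitalization for heart failure. Rewording the consent condition would not act retroactively on the 5,812 subjects already recruited.

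**Cost.** SAP wording, one derived date, one by-arm table and one repeated analysis. SAP 2.3.2 already refers to endpoint event status in the eCRF, so much of the source date appears to be available. The downside is that a few late-found CV deaths may leave one version of the composite analysis.

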### 2.3.3. Visit Windows

The Time and Events Schedule of the protocol indicates the visit timing and procedures (eg, laboratory, vital signs, and other key safety variables) for each visit; however, the timing of a subject's actual visit may not be exactly as per the protocol indicated target day / visit window. Consequently, for by-visit or over-time summaries, depending on the time period(s) involved in the summaries, the conventions outlined below will be used to allocate the data collected at each actual visit to a planned protocol visit by defining visit windows.

Baseline will be defined as the pre-dose measurement closest to or including Day 1 (prior to dose administration). If the pre-dose measurement on Day 1 is missing, the missing value will be imputed by the latest available measurement prior to Day 1. For serum creatinine, the average of the last 2 pre-dose measurement will be used as baseline.

If a subject has 2 or more actual visits in one analysis visit window, the visit closest to the target day will be used as the study visit for that analysis visit window. However, results from all visits will be included in the safety analyses (eg, pre-defined limits of change analysis) to assure that all results are included. If 2 study visits are the same number of days from the target day within the same visit window, the later visit will be considered the study visit for that target day. Even though all visits will be allocated an analysis visit window, only planned protocol visits for each variable will be included in the by-visit summaries or repeated measure analyses.

Note that the algorithms for calculating visit windows are the same for all the data periods (see Table 1). Table 2 summarizes the analysis visit windows for laboratory, vital signs, and other key safety variables.

**Table 2: Time Intervals for Analysis (in clinic) Visit Windows**

Scheduled Visit Time (label on output)	Time Interval (Day) a	Target Time Point (Day)
Baseline	≤1 b	1
Week 13	1 c –137	92
Week 26	138–229	183
Week 52	230–456	365
Week 78	457–638	547
Week 104	639–820	729
Week 130	821–1002	911
Week 156	1003–1184	1093
Week 182	1185–1366	1275
Week 208	1367–1548	1457

a Relative to the day of the first dose of double-blind study drug.

b Up to the first dose of double-blind study drug.

c Immediately following the first dose of double-blind study drug. For variables with no time or reference collected at baseline, the first window after baseline starts on Day 2 according to the protocol.

### 3. SUBJECT INFORMATION

#### 3.1. Baseline Anthropometric and Demographic Characteristics

Baseline anthropometric and demographic characteristics will be summarized by treatment group. Descriptive statistics (N, mean, standard deviation [SD], median, and range) will be provided by treatment group for the baseline age and baseline body weight.

Additionally, the number and percentage of subjects in the categories of the following variables at baseline will also be summarized by treatment group:

- Age group: <65, ≥65 years old;
- Sex: Male, Female;
- Race: White, Black or African American, Asian, Others;
- Ethnicity: Hispanic or Latino, Not Hispanic or Latino, Unknown, Not reported;
- Region: North America, Central/South America, Europe, Rest of the World.

#### 3.2. Baseline Disease Characteristics

Descriptive statistics (N, mean, SD, median, and range) will be provided by treatment group and overall for the following baseline continuous variables: duration of diabetes (in years), baseline eGFR, baseline ACR, systolic blood pressure (SBP), weight, body mass index (BMI), HbA1c, LDL-C, HDL-C, triglycerides, total cholesterol and LDL-C/HDL-C.

Additionally, the number and percentage of subjects will be summarized by treatment group and overall for the following:

- Baseline BMI categories (<30, ≥30 kg/m^2);
- Currently daily cigarette smoker: Yes/No;
- Baseline HbA1c ≥ 8%: Yes/No;
- Duration of T2DM ≥ 10 years: Yes/No;
- Baseline systolic blood pressure categories (≤140, >140 mmHg);
- Baseline LDL-C categories (≤70, >70 mg/dL);
- Baseline HDL-C categories (<39, ≥39 mg/dL);
- Baseline eGFR categories (<30, 30 to <60, 60 to <90, ≥90 mL/min/1.73m^2);
- Baseline albuminuria category:
  - Normoalbuminuria (0 ≤ ACR <30 mg/g); Microalbuminuria (ACR ≥30 mg/g and ≤300 mg/g); Macroalbuminuria (ACR >300 mg/g: ACR >300 mg/g and ≤3000 mg/g, ACR > 3000 mg/g).
- History of hypertension: Yes/No ;
- History of CV disease: Yes/No;

- History of coronary artery disease: Yes/No;
- History of cerebrovascular disease: Yes/No;
- History of peripheral vascular disease: Yes/No;
- History of heart failure: Yes/No;
- Microvascular diabetes complications (Any, 1, 2 or 3 of retinopathy, neuropathy [diabetic or automatic neuropathy] and nephropathy)
- History of fracture: Yes/No;

The number and percentage of subjects with a history of medical conditions by system organ class and preferred term (based upon the general medical history eCRF) will be summarized by treatment group and overall.

### **3.3. Disposition Information**

Disposition will be summarized for all randomized subjects by treatment group using the categories listed below:

- Screen failure;
- Subjects who are randomized (ITT);
- Subjects who are treated;
- Subjects who completed the study (ie, defined as having been followed until a time point between the notification of the GTED and the GTED, or if the subject had died prior to the GTED);
- Subjects who prematurely discontinued study medication;
- Subjects without final vital status.

The reasons for non-randomization, withdrawal from study (eg, lost to follow-up, consent withdrawal), and discontinuation from study medication will be summarized. The distribution of time to premature discontinuation of study medication will be displayed using a Kaplan-Meier plot, where one minus the survival function will be shown.

Listings will be provided for subjects whose predominant treatment differs from their randomized treatment.

### **3.4. Extent of Exposure and Follow-Up**

Total exposure time for each subject is defined as the number of days from Day 1 to the last dose date (inclusive), regardless of any temporary drug interruption(s). Follow-up time is defined as the number of days from Day 1 to the last contact day (inclusive) for each subject. Descriptive statistics (N, mean, SD, median, and range) for total exposure or follow-up time will be presented by treatment group.

The number of subjects with duration in each of the following categories (<13 weeks, 13 to <26 weeks, 26 to <52 weeks, 52 to <104 weeks, 104 to <156 weeks, ≥156 weeks) will also be presented by treatment group as well as overall.

